13.5.3. Exploratory Efficacy Analysis

All exploratory efficacy endpoints will be analyzed descriptively at given scheduled visit if applicable. These descriptive analyses may include statistical tests depending on the type of data. No multiplicity will be done for the exploratory efficacy analyses

13.5.4. Multiplicity Considerations

The overall Type-1 error rate of 0.05 (2-sided) will be controlled for the primary endpoint and the first secondary endpoint (ie, change in the cumulative tolerated dose [log transformed] of milk protein during a DBPCFC from baseline to week 18) using a hierarchical testing procedure. Inferential conclusions about the first secondary endpoint require statistical significance at the 2-sided 0.05 significance level of the primary endpoint.

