13.1. Statistical Hypothesis

The primary efficacy endpoint is the proportion of subjects who tolerate a cumulative dose of at least 2040 mg milk protein during a DBPCFC at week 18. The comparison between the dupilumab plus milk OIT arm (Cohort A) and the placebo plus milk OIT (Cohort B) arm will be made.

Letting p_D (and p_P) be the true proportion of subjects who tolerate a cumulative dose of at least 2040 mg milk protein during a DBPCFC at week 18 in the treatment arms of dupilumab + milk OIT and placebo + milk OIT, respectively. The following hypothesis for the superiority testing will be tested at the 5% 2-sided significance level:

$H_0: p_D = p_P$, i.e. the proportion of subjects who tolerate a cumulative dose of at least 2040 mg milk protein during a DBPCFC at week 18 is the same between dupilumab + OIT arm and the placebo + OIT arm

against the alternative

$H_a: p_D \neq p_P$, i.e. the proportion of subjects who tolerate a cumulative dose of at least 2040 mg milk protein during a DBPCFC at week 18 are different between the dupilumab + OIT arm and the placebo + OIT arm

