13.5.1. Primary Efficacy Analysis

The primary endpoint will be analyzed using the Cochran-Mantel-Haenszel (CMH) test adjusted by randomization stratification factor (study site) to assess the treatment difference in the proportion of responders in the FAS. Estimate of treatment difference, p-value, and the 2-sided 95 % confidence interval will be calculated.

If a subject withdraws from study, the subject will be counted as a non-responder at time points after study withdrawal. The subject will also be considered a non-responder at the time point when data are missing. All observed data will be used for primary analysis.

Sensitivity analyses utilizing alternative methods for handling missing data will be performed to assess the robustness of the primary analysis result. Alternative methods may include complete case analysis (observed value analysis). Details will be specified in the statistical analysis plan (SAP).

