13.5.5. First-Step Analysis

A first-step analysis may be performed when the last subject completes 24 weeks of the treatment period as specified in the protocol. No changes in the conduct of the study will be made based on this first-step analysis. The assessment of primary and secondary endpoints up to week 24 and performed during the analysis will be the final analysis of the primary endpoint and the secondary endpoints up to week 24. Hence there will be no need for alpha adjustment due to the first-step analysis. If a decision is made to perform the first-step analysis, in order to maintain study integrity with respect to the washout phase and the post-treatment follow-up visits, and analyses, a dissemination plan will be written. This plan will clearly identify the team (including the statistician) that will perform the first-step analysis and all related activities, restrict other clinical team members and other sponsor personnel from access to individual subject treatment allocation and site level analysis results, and ensure that the dedicated team will not participate in the data review or data decisions for the following post treatment analyses. However, the dedicated team can participate in the analysis following the final database lock.

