13.8. Interim Analyses

Interim analyses to investigate the primary efficacy endpoint are planned after the first 40 participants (20 per arm) are enrolled and complete their Week 18 DBPCFCs. The interim analysis is designed to allow for early stopping when we reject the null hypothesis with a significant difference in the proportions of participants who tolerate a cumulative dose of at least 2040 mg

milk protein during the Week 18 DBPCFCs between the two treatment arms. The O'Brien-Fleming decision boundary is used to control the overall type I error probability at the conventional 0.05 level. The Lan-DeMets error-spending approach that approximates O'Brien-Fleming is used to determine the alpha with the information fraction of 45.5% (40 out of 88 participants). At the interim analysis stage, the null hypothesis will be rejected if the test is significant at the alpha level of 0.002 with an associated absolute Z statistic of 3.13. Thus, the trial will be stopped if the test statistic is less than or equal to -3.13 or greater than or equal to 3.13 with a p value ≤ 0.002 ; otherwise, the null hypothesis will be accepted and the trial will be continued.

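### The plan spends alpha at an efficacy look but states no final boundary, and 13.5.4 still tests the primary endpoint at an unadjusted 0.05

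*Combined protocol and SAP*

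**What the plan says.** - **13.8 Interim Analyses.** The look may stop the trial by rejecting the null hypothesis. The O'Brien-Fleming boundary "is used to control the overall type I error probability at the conventional 0.05 level". The spending calculation uses an "information fraction of 45.5% (40 out of 88 participants" and gives an interim level of 0.002 and |Z| of 3.13. If the boundary is not crossed, "otherwise, the null hypothesis will be accepted and the trial will be continued". No critical value or nominal level follows for the final test.
- **13.1 Statistical Hypothesis.** "The following hypothesis for the superiority testing will be tested at the 5% 2-sided significance level".
- **13.5.4 Multiplicity Considerations.** The first sentence says that the overall two-sided 0.05 is controlled across the primary and the first secondary endpoint. The last sentence gives the working rule: "Inferential conclusions about the first secondary endpoint require statistical significance at the 2-sided 0.05 significance level of the primary endpoint". The interim look is not mentioned.
- **13.5.1 Primary Efficacy Analysis.** The test is the "Cochran-Mantel-Haenszel (CMH) test adjusted by randomization stratification factor (study site", with no significance level given.
- **13.5.5 First-Step Analysis.** It says that "there will be no need for alpha adjustment due to the first-step analysis". This covers the analysis after the last subject reaches week 24, not the look in 13.8.

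**The concern.** Once some of the 0.05 has been spent at a look that can reject the null hypothesis, the final test cannot also use the full 0.05 if the total is to stay at 0.05. The plan names the spending function but stops short of the final boundary. The only operational level printed for the primary test is the unadjusted one.

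Two careful analysts could therefore use different thresholds. One, following the last sentence of 13.5.4, would use p ≤ 0.05. The other, working from 13.8, would derive p ≤ 0.0494. The same number decides the primary claim and whether the first secondary endpoint can be tested, so a result between the two thresholds would have to be settled after unblinding.

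**Working it through.** **Inputs.** Overall two-sided alpha 0.05 (13.1, 13.5.4, 13.8); t = 40/88 = 0.4545 and interim |Z| 3.13 (13.8); 58 per arm, 20% vs 55%, 25% dropout (13.2).

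**1. Reproduce the interim figure.** The two-sided O'Brien-Fleming-type spending function is

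α₁ = 4[1 − Φ(z₀.₉₈₇₅/√t)].

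With z₀.₉₈₇₅ = 2.2414 and √t = 0.6742, the ratio is 3.3245 and the upper tail is 0.000443. So α₁ = 4 × 0.000443 = 0.00177, which is |Z| = 3.126. This agrees with the printed 3.13 and 0.002 and identifies the spending function in use.

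**2. Final boundary implied by 13.8.** Under the null hypothesis the interim and final statistics are taken as bivariate normal with correlation √t = 0.6742. Solving

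1 − P(|Z₁| < 3.126, |Z₂| < c) = 0.05

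gives c = 1.965, a nominal two-sided p of 0.0494.

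**3. Overall error if 0.05 is used at the end.** With |Z| ≥ 3.13 at the look:
- final |Z| ≥ 1.960: overall error 0.0506;
- final |Z| ≥ 1.965: overall error 0.0500.

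The nominal excess is 0.0506 − 0.0500 = 0.0006.

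**4. Comparison with discreteness.** Exact enumeration, unstratified, 20 per arm at the look and 58 per arm at the end, gives these overall errors by common response rate:
- 15%: 0.0465
- 20%: 0.0487
- 30%: 0.0517
- 50%: 0.0516

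They are the same under 1.960 and 1.965, because no unstratified 58/58 table falls between the two values. These departures from 0.05, in both directions, exceed 0.0006.

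**5. Can the two thresholds give different verdicts?** Yes. With slightly unequal arms, 4 tables fall between them at 57/58 and 6 at 59/57. For example, 27/59 vs 16/57 gives Z = 1.964, p = 0.0495.

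Under the planned site-stratified test they can differ at 58/58 as well. This was simulated with 6 million trials per case, four assumed per-arm site splits (20/19/19, 34/12/12, 29/29, 40/18; the documents give none) and seven common rates from 15% to 50%, so 28 cases:
- null probability of falling between the thresholds: under 0.0001 to 0.0031;
- overall error with 1.960: 0.0477 to 0.0519;
- overall error with 1.965: 0.0473 to 0.0515.

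**6. Power cost at 58 per arm.** The drift is (p_D − p_P)/√{[p_D(1−p_D) + p_P(1−p_P)]/58}.
- 55% vs 20%: drift 4.176; power 98.67% with 1.960 and 98.65% with 1.965.
- Each rate multiplied by 0.75, if all dropouts count as non-responders (41.25% vs 15%): drift 3.287; power 90.8% and 90.7%.

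**The case against.** The strongest reply is that nothing printed is wrong. Section 13.8 gives the spending function, the fraction and the overall level, and these fix one final boundary. The 5% in 13.1 and the first sentence of 13.5.4 can both be read as the overall level. Section 13 also describes itself as the basis for a final SAP to be issued before lock and unblinding, where the number could be given. Much of this stands, and a reader who infers that the sections flatly contradict each other goes too far. What remains is the last sentence of 13.5.4. It is a decision rule for the primary test, and followed as written after the look it does not deliver the overall 0.05 claimed in the same section and in 13.8.

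A second reply is that the excess has no practical weight. At the plan's own control rate of 20%, and at 15% after non-responder counting, the exact unstratified error is below 0.05 even with 1.960. Nor does 1.965 guarantee control: in the simulated stratified cases, error still exceeded 0.05 in 4 of 28, all at a common rate of 50%. This stands too. It limits the size of the point, but it does not remove the need for a single stated threshold.

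**Conclusion.** The point holds as a small but real gap in the decision rule. No final boundary is stated, and the one operational level given for the primary test and for entry to the first secondary endpoint is unadjusted for the look. Taken literally, the nominal overall error is 0.0506, an excess of 0.0006. The practical stake is confined to a final p between about 0.0494 and 0.05. The figures rest on normal theory at t = 40/88; the stratified results also rest on assumed site splits.

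Three stronger readings are not supported:
- **That type I error is materially inflated.** Discreteness moves it by more than the missing adjustment does.
- **That the interim boundary is miscalculated.** The printed figures reproduce.
- **That the null hypothesis is finally accepted at a non-significant look.** The wording in 13.8 is loose, but its instruction is to continue.

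Whether the information fraction should be based on 88, or on the 116 in the full analysis set with non-responder counting, is a separate question and adds no weight here.

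**What to change.** - **13.1 and 13.5.4:** state that 0.05 is the overall two-sided level. State also that the final primary test, and entry to the first secondary endpoint, use the final boundary from the spending function named in 13.8: |Z| ≥ 1.965, two-sided p ≤ 0.0494 at the planned 40/88. Recompute it from the actual information fraction, on one denominator fixed before the look.
- **13.8:** print that final boundary, and say that a result short of the interim boundary means the null hypothesis is not rejected at the look and the trial continues to the final test.

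Optional clarifications: label the interval in 13.5.1 ("Estimate of treatment difference, p-value, and the 2-sided 95 % confidence interval will be calculated") as nominal or match it to the final level, and state the level for the first secondary endpoint if the trial stops at the look.

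The cost is a few sentences, in the protocol or the final SAP, with the denominator settled before the look. Power falls by less than 0.1 percentage point and the sample size does not change.

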13.5.5. First-Step Analysis

A first-step analysis may be performed when the last subject completes 24 weeks of the treatment period as specified in the protocol. No changes in the conduct of the study will be made based on this first-step analysis. The assessment of primary and secondary endpoints up to week 24 and performed during the analysis will be the final analysis of the primary endpoint and the secondary endpoints up to week 24. Hence there will be no need for alpha adjustment due to the first-step analysis. If a decision is made to perform the first-step analysis, in order to maintain study integrity with respect to the washout phase and the post-treatment follow-up visits, and analyses, a dissemination plan will be written. This plan will clearly identify the team (including the statistician) that will perform the first-step analysis and all related activities, restrict other clinical team members and other sponsor personnel from access to individual subject treatment allocation and site level analysis results, and ensure that the dedicated team will not participate in the data review or data decisions for the following post treatment analyses. However, the dedicated team can participate in the analysis following the final database lock.

13.6. Safety Analysis

13.6.1. Adverse Events

Definitions

For safety variables, 2 observation periods are defined:

- The pretreatment period is defined as the time from signing the ICF to before the first dose of study drug.
- The treatment period is defined as the day from first dose of study drug to the end of the study.

Treatment-emergent adverse events are defined as those that are not present at baseline or represent the exacerbation of a pre-existing condition during the on-treatment period.

Analysis

All AEs reported in this study will be coded using the currently available version of the CTCAE. Coding will be to lowest level terms. The verbatim text, the preferred term (PT), and the primary system organ class (SOC) will be listed.

Summaries of all AEs by treatment group will include:

- The number and percentage of subjects with at least 1 AE by SOC and PT
- AEs by severity, presented by SOC and PT
- AEs by relationship to treatment (related, not related), presented by SOC and PT
- Treatment-emergent AESIs (defined with a PT or a prespecified grouping)

Deaths and other SAEs, as well as AEs leading to permanent treatment discontinuation, will be listed and summarized by treatment group.

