--	---

Primary Endpoint	Proportion of subjects treated with dupilumab plus milk protein OIT vs placebo plus milk protein OIT who tolerate at least 2040 mg (cumulative) cow's milk protein during DBPCFC to milk at week 18
Secondary Endpoints	
Clinical
 
 Proportion of participants who tolerate at least 1040 mg cumulative milk protein at week 18 DBPCFC Proportion of participants who tolerate 4040 mg cumulative milk protein at week 18 DBPCFC Proportion of participants who tolerate at least 1040 mg cumulative milk protein at week 24 DBPCFC Proportion of participants who tolerate at least 2040 mg cumulative milk protein at week 24 DBPCFC Proportion of participants who tolerate 4040 mg cumulative milk protein at week 24 DBPCFC Change in the cumulative tolerated dose (CTD) of milk protein during DBPCFC from baseline to week 18 and baseline to week 24 across cohorts as pairwise comparisons of all treatment groups 
 Due to the positive skew for the distribution of the CTD, a log transformation will be applied to reduce the skewness 
Safety
 
 The rate and severity of OIT-induced gastrointestinal symptoms in subjects receiving dupilumab compared to placebo. Proportion of participants who have OIT-induced gastrointestinal symptoms, dupilumab compared to placebo The rate and severity of AEs, SAEs, and safety events in each cohort Proportion of participants completing the study among cohorts 
Exploratory and Mechanistic
 
 Change from baseline to week 24 in the log-transformed minimum concentration of milk protein which activates basophils, comparison between dupilumab and placebo Percent change from baseline to week 24 in milk-specific and total IgE and milk-specific and total IgG4, comparison between dupilumab and placebo Percent change from baseline to week 24 in milk SPT response, comparison between dupilumab and placebo Proportion of subjects experiencing esophageal eosinophilia, dupilumab compared to placebo, if data is available
Procedures and Assessments	The efficacy of dupilumab will be assessed by DBPCFC at week 18 (primary and secondary) and week 24 (secondary). Overall safety will be assessed by monitoring/evaluation of allergic reactions, treatment-emergent adverse events (TEAEs), physical examinations, and vital signs at pre-specified time points.

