8.2. Screening/Baseline Visits (V1)

The purpose of the screening period is to confirm eligibility to continue in the study. After obtaining informed consent/assent, subjects will be assessed for eligibility at a screening visit. Procedures for the screening visit may be spread over one to three separate days; these days do not need to be consecutive and can be spread out over the course of the entire screening window. All assessments must be completed no more than 6 months preceding initiation dupilumab/placebo (Visit 2, week 0), excluding the milk-specific IgE value which may be taken from the previous 12 months if needed to establish eligibility. Baseline/screening visit procedures following requirements below but conducted under a different protocol within the past 6 months (or 12 months for milk-specific IgE) prior to Visit 2 can be used towards this study. Visit 1 may occur on the same day as Visit 2, but must be completed prior to any Visit 2 procedure taking place.

The following procedures, assessments, and laboratory measures will be conducted to determine participant eligibility and collect baseline data:

- Consent and assent (conducted prior to any screening or study procedure)
- Medical history, including review of all food allergies
- Physical assessment
- Documentation of con meds and AEs
- Epinephrine auto-injector training with Food Allergy & Anaphylaxis Emergency Care Plan
- SPT to cow's milk (only if needed to determine eligibility)
- Lung function (spirometry, or peak flow if spirometry not available, applicable, or able to be performed reliably by the participant). If spirometry and peak flow are both unable to be completed, defer to clinician judgment
- Urine pregnancy test in women of childbearing potential (WOCBP)

Any of the above items may be repeated within the 6 months preceding initiation of study treatment if warranted, in the opinion of the investigator, by changes in the subject's clinical status. After all other eligibility criteria have been met, DBPCFCs to a cumulative 444 mg of milk and placebo (oat)

Double-Blind Placebo-Controlled Food Challenge (DBPCFC) at Screening

Participants meeting all other eligibility criteria will undergo DBPCFC to cow's milk protein and oat (placebo) during screening to confirm an allergy to milk. Randomization of the placebo and

milk challenge order and preparation of the challenge materials will be performed by trained unblinded study personnel.

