11.4. Collection and Recording of Adverse Events

11.4.1. Collection Period

AEs will be collected from the time of consent until a participant completes study participation or until 30 days after he/she prematurely withdraws (without withdrawing consent) or is withdrawn from the study. Ongoing AEs at the time of study completion will be followed for 30 days or until the time of resolution, whichever occurs first. SAE information will be collected until the event is considered chronic and/or stable.

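### The AE tables in Section 13.6.1 are not limited to treatment-emergent events, so as written they count pre-drug AEs and dilute the percentage-with-an-AE comparison

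*Combined protocol and SAP*

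**What the plan says.** Section 13.6.1 sets up the definitions needed for treatment-emergent reporting:

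- Pretreatment period: "The pretreatment period is defined as the time from signing the ICF to before the first dose of study drug".
- Treatment period: from the first dose of study drug to the end of the study.
- TEAEs: "Treatment-emergent adverse events are defined as those that are not present at baseline or represent the exacerbation of a pre-existing condition", with the exacerbation tied to an on-treatment period, a term the section does not define.

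The table list that follows does not use them. It opens with "Summaries of all AEs by treatment group will include". The main incidence table is "The number and percentage of subjects with at least 1 AE by SOC and PT". The severity and relationship tables are also of AEs without qualification. The one line limited by period is "Treatment-emergent AESIs (defined with a PT or a prespecified grouping" and so on. Deaths, other SAEs and AEs leading to permanent discontinuation are to be listed and summarized by treatment group, with no period stated.

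Section 11.4.1 fixes when AE data begin: "AEs will be collected from the time of consent until a participant completes study participation". Section 8.2 allows screening assessments to be up to 6 months old at Visit 2, and also allows Visit 1 and Visit 2 on the same day.

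Two other places describe the safety comparison differently. The synopsis, under Procedures and Assessments, says: "Overall safety will be assessed by monitoring/evaluation of allergic reactions, treatment-emergent adverse events (TEAEs), physical examinations, and vital signs" at set time points. The secondary safety objective in Section 2.3 compares allergic and non-allergic AEs phase by phase.

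**The concern.** An event before the first injection cannot be an effect of dupilumab. Randomization takes place at Visit 2, so such events are expected equally in both arms. Counting them in a by-arm percentage raises both percentages and brings them closer together. That can hide a benefit as easily as a harm.

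This matters because the AE comparison is one of the trial's stated aims. The hypothesis in Section 2.1 includes fewer and milder AEs with dupilumab, and Section 3.5.2 makes AE rate and severity secondary safety endpoints. An analyst who follows the table list literally would produce tables that deliver neither the synopsis statement nor the by-phase objective. If the gap is noticed only after unblinding, someone must choose between two versions of the AE table with the results in view.

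**Working it through.** The safety section states no figure, so there is nothing to reproduce. The check is a reading of the text followed by the arithmetic of dilution.

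**Step 1. Does anything else limit event dates?**

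| Place | What it does | Removes pre-drug events? |
|---|---|---|
| 11.4.1 Collection Period | Starts AE collection at consent | No |
| 13.3.2 Safety Analysis Set | Limits people to those randomized and dosed | No; it limits people, not dates |
| 11.3.1 Grading Criteria | Records screening-to-baseline grade changes as AEs, but not treatment-emergent | No; it confirms that pre-drug AEs are in the data |
| 13.6.1, AESI line | Limits AESIs to treatment-emergent | Yes, for AESIs only |
| 11.2.1 Adverse Event | Records expected challenge reactions within two hours as dosing reactions, not AEs | Partly; most screening-challenge reactions stay out |

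As written, the incidence, severity, relationship, SAE and discontinuation summaries can contain pre-drug events.

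**Step 2. Dilution of a percentage row.** Let p be the on-treatment probability of the event in an arm and q the pre-drug probability, equal in both arms and independent of the on-treatment event. Then

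P(at least one AE) = 1 − (1 − q)(1 − p),

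and the between-arm difference is (1 − q)(p_placebo − p_dupilumab). Without independence, the factor (1 − q) applies to the risk difference among participants who had no pre-drug event.

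**Step 3. Numbers.** Inputs:

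- On-treatment GI rate with OIT alone: 40% (Section 1.1).
- Rate with dupilumab: 20% (assumption).
- q: assumed, because the documents give none.
- 58 per arm (Section 13.2). Power is for a two-sided 5% comparison of two proportions and is illustrative only, since Section 13.6 plans no safety test.

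| q | Placebo + OIT | Dupilumab + OIT | Difference (points) | Risk ratio | Power |
|---|---|---|---|---|---|
| 0 (TEAEs only) | 40% | 20% | 20 | 0.50 | 66% |
| 5% | 43% | 24% | 19 | 0.56 | 58% |
| 20% | 52% | 36% | 16 | 0.69 | 41% |
| 40% | 64% | 52% | 12 | 0.81 | 26% |

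Example at q = 20%: 1 − 0.8 × 0.6 = 0.52 and 1 − 0.8 × 0.8 = 0.36, a difference of 0.16.

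**Step 4. Event counts behave differently.** Suppose the placebo rate is 1 unit per week over 24 weeks, the dupilumab rate is half that, and the pre-drug rate is a quarter of the placebo rate over 26 weeks (all assumed for illustration). Totals are 24 + 6.5 = 30.5 and 12 + 6.5 = 18.5. The absolute difference stays at 12; the ratio moves from 0.50 to 18.5/30.5 = 0.61.

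**Step 5. What bounds q.** Six months is about 26 weeks, so at most 26/(26 + 24) = 52% of a participant's AE observation time is pre-drug. With same-day screening the share is close to zero. This share does not enter the formula; q does. What remains to produce pre-drug AEs is challenge reactions after two hours, skin-test or blood-draw events that meet the short lists in Section 11.2.1, and intercurrent illness. The planned tables are by SOC and PT, so q must be taken row by row and is likely small for a single PT.

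**The case against.** The strongest reply is that this is loose drafting that nobody would follow literally. The definitions stand directly above the table list, the synopsis names TEAEs, the objective is by phase, and Section 11.3.1 separates pre-baseline changes. Section 13.7 also places AEs with incomplete start dates relative to first dose, a rule that matters mainly if events are split there. Section 13 is described as the basis for an SAP to be finalized before lock and unblinding, the tables are descriptive, and onset dates would allow a TEAE cut. All of this stands as evidence of intent. It makes the correction uncontroversial, but it does not make the written list right.

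Three stronger readings are tempting, and the documents do not support them:

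- **That pooling was a deliberate choice.** The contrast with the AESI line invites this, but the places just listed point the other way.
- **That six months of pre-drug events, including a challenge reaction in every participant, load the tables.** Six months is a limit on the age of assessments and same-day screening is allowed. Expected challenge reactions within two hours are dosing reactions. The skin test at Visit 1 is done only if needed for eligibility.
- **That every real safety difference is shrunk.** AESIs are already limited, pre-drug events should rarely be judged related to study drug, and absolute differences in event counts do not change.

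**Conclusion.** The point holds as an inconsistent specification. Read as written, Section 13.6.1 puts pre-drug events into the by-arm incidence and severity tables, leaves the SAE and discontinuation summaries without a period, and does not match the synopsis or the by-phase objective.

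The direction of the effect is clear for percentage-with-an-AE rows: the risk difference is multiplied by (1 − q). The size cannot be derived from the documents. The 19, 16 and 12 points rest on assumed values of q, an assumed 20% rate with dupilumab, and independence of pre-drug and later events. The larger values of q are more plausible for an overall any-AE row than for a single PT, where the effect is probably small. Since the aim is to compare AEs and the correction is cheap, it should be made before unblinding.

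**What to change.** In Section 13.6.1 and the final SAP:

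1. State that the incidence, severity, relationship, SAE and discontinuation summaries are of TEAEs, meaning onset or worsening on or after the first dose of study drug, in the safety analysis set.
2. List pretreatment AEs separately.
3. Use one defined term in place of treatment period and on-treatment period. The last injection is at week 16 and the study ends at week 24, so the definition should say whether the final 8 weeks count.
4. Add summaries by study phase (run-in, combination therapy, washout) to match the objective in Section 2.3.

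The cost is a few sentences and a few more tables. No new data are needed, and Section 13 allows revision of the SAP before the database is locked and unblinded.
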